9.3. Populations for Analyses

The following populations are defined:

Population	Description
Entered/Enrolled Population	All participants who sign the ICF
Randomized Population	All participants assigned to treatment, regardless of whether they take any doses of study treatment, or if they took the correct treatment. The participants previously randomized to Algorithm 2 will be pooled with the participants randomized to Algorithm 1 and all of these participants will be analyzed as one treatment group of LY3209590.
Efficacy Population	Participants in randomization population excluding the participants previously randomized to Algorithm 2.
Safety Population	All participants randomly assigned to study treatment and who take at least 1 dose of study treatment. The participants previously randomized to Algorithm 2 will be pooled with the participants randomized to Algorithm 1 and all of these participants will be analyzed as one treatment group of LY3209590.
Pharmacokinetic Population	All randomized participants who received at least 1 dose of LY3209590 and have at least 1 evaluable PK sample.

Abbreviations: ICF = informed consent form; PK = pharmacokinetics.

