9.4. Statistical Analyses

Statistical analysis of this study will be the responsibility of sponsor or its designee.

All tests of treatment effects will be conducted at a 2-sided alpha level of 0.1, unless otherwise stated, and all confidence intervals (CIs) will be given at a 2-sided 90% level.

Any change to the data analysis methods described in the protocol will require an amendment only if it changes a principal feature of the protocol. Any other change to the data analysis methods described in the protocol, and the justification for making the change, will be described in the statistical analysis plan (SAP) and the clinical study report. Additional exploratory analyses of the data will be conducted as deemed appropriate.

The SAP will include a more technical and detailed description of the statistical analyses described in this section. This section is a summary of the planned statistical analyses of the most important endpoints including primary and key secondary endpoints.

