9.4.1. General Considerations

Unless otherwise stated, the efficacy analyses will be conducted on efficacy analyses set (EAS) based on the Efficacy Population using the data up to the study treatment discontinuation (defined as the observed data with collection date before or at the last dose date +10 days). Sensitivity analyses for selected efficacy measures may be conducted on the Randomized Population using the data up to the study treatment discontinuation.

Unless otherwise stated, the safety analyses except for hypoglycemia will be conducted on the safety analyses set based on the Safety Population using all data collected during the study including treatment and follow-up period regardless of the treatment disposition status. The details for analyses of hypoglycemia will be documented in the SAP.

Unless otherwise specified, the baseline value used for the analyses will be the last nonmissing value obtained for each participant prior to or on the date of first study IP dose (or randomization visit date if first dose date is missing). The baseline liver enzyme lab measures will be the average of all assessments prior to and at randomization visit.

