9.4.6.3. Hypoglycemia Episodes

The incidence and rate per year of hypoglycemia will be presented for the periods between 0-12 weeks, 12-26 weeks, 0-26 weeks, and the follow-up period and analyzed according to the hypoglycemia definitions described in the American Diabetes Association classification system (ADA 2019). The analyses for hypoglycemia will be performed on Efficacy Population and additionally the severe (level 3) hypoglycemia analysis will also be performed for the Safety Population.

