5.1. General Considerations

All data will be entered, verified, and archived at a contract research organization (CRO) external to Eli Lilly and Company (Lilly) and/or at Lilly. Data listings, summaries, and analyses will be performed by a CRO and/or by Lilly under the guidance and approval of statisticians at Lilly.

Statistical analysis of this study will be the responsibility of sponsor or its designee. Any change to the data analysis methods described in the protocol will require an amendment only if it changes a principal feature of the protocol. Any other change to the data analysis methods described in the protocol, and the justification for making the change, will be described in this SAP and/or the clinical study report(CSR). Additional exploratory analyses of the data will be conducted as deemed appropriate.

The following populations are defined for purpose of analysis:

Population	Description
Entered/Enrolled Population	All participants who sign the ICF
Randomized Population	All participants assigned to treatment, regardless of whether they take any doses of study treatment, or if they took the correct treatment. The participants previously randomized to LY3209590 Algorithm 2 will be pooled with the participants randomized to Algorithm 1 and all of these participants will be analyzed as one treatment group of LY3209590.
Efficacy Population	All participants randomized to either LY3209590 Algorithm 1 or insulin degludec and took at least 1 dose of study treatment. Participants will be analyzed according to the treatment they were assigned.
Safety Population	All participants randomly assigned to study intervention and who took at least 1 dose of study treatment. The participants previously randomized to LY3209590 Algorithm 2 will be pooled with the participants randomized to Algorithm 1 and all of these participants will be analyzed as one treatment group of LY3209590.
Pharmacokinetic Population	All randomized participants who received at least 1 dose of LY3209590 and have at least 1 evaluable PK sample.

Abbreviations: ICF = informed consent form; PK = pharmacokinetics.

Unless otherwise stated, the efficacy analyses will be conducted on efficacy analyses set (EAS) based on the Efficacy Population using the data up to the study treatment discontinuation

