Incidence of hypoglycemia events for Level 1 and Level 2/3 
 • Documented • Nocturnal • Non-Nocturnal 	0-12, 0-26, 12-26 weeks, post-treatment period (up to Visit 801)*	Logistic regression with treatment, baseline HbA1c, baseline hypoglycemia incidence for the same type of the dependent variable in the model.

 • Proportion of patients with HbA1c <7% without documented nocturnal hypoglycemia event (Level 1 and Level 2) • Proportion of patients with HbA1c $\leq 6.5\%$ without documented nocturnal hypoglycemia event (Level 1 and Level 2) 	0-26 weeks	Logistic regression with treatment, country, baseline HbA1c, and baseline nocturnal hypoglycemia incidence in the model.

Abbreviations: HbA1c = hemoglobin A1c; Level 2/3 = Level 2 and Level 3 composite.

Note: The hypoglycemia rate per year during defined period is calculated by the number of hypoglycemia within the period/number of days patient at risk within the period*365.25 days. The hypoglycemia incidence during defined period indicates if the patient has at least 1 hypoglycemia events within the period (Yes/No). The baseline hypoglycemia rate is the rate calculated between Visit 2 and Visit 3.

*Analyses for endpoint during post-treatment period (up to Visit 801) will include all of the data after study drug discontinuation on Safety population; analyses for endpoints during other time points will include all data before study drug discontinuation on Safety population.

The following is the example of the SAS code of the negative binomial regression for analyzing the rate of hypoglycemia events.

```

proc glimmix empirical data=DATA;
  class TREATMENT;
  model HYPO_FREQ=TREATMENT [BASELINE_HYPO]
    /dist=nb link=log offset=log(exposure in
    days/365.25);
    lsmeans TREATMENT/OM pdiff cl alpha=0.1 ilink;
    random _residual_;
run;

```

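### The SAP puts diary hypoglycemia on the pooled Safety Population, the protocol specifies the Efficacy Population without Algorithm 2, and the SAP does not declare the change

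*SAP*

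**What the plan says.** **Protocol.** Section 9.4.6.3 states: "The analyses for hypoglycemia will be performed on Efficacy Population and additionally the severe (level 3) hypoglycemia analysis will also be performed". The sentence goes on to name the Safety Population as the one used for that level 3 addition. Section 9.4.1 agrees with this by taking hypoglycemia out of the safety default: "the safety analyses except for hypoglycemia will be conducted on the safety analyses set based on the Safety Population". It then leaves the details of the hypoglycemia analyses to the SAP. Section 9.3 defines the Efficacy Population as "Participants in randomization population excluding the participants previously randomized to Algorithm 2". Section 9.4 sets the rule for non-principal changes of method: the change, "and the justification for making the change, will be described in the statistical analysis plan (SAP) and the clinical study report".

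**SAP.** Section 5.1 repeats the safety default without the exception for hypoglycemia. It says of the Safety Population: "The participants previously randomized to LY3209590 Algorithm 2 will be pooled with the participants randomized to Algorithm 1". Section 5.10 makes pooled LY3209590 versus insulin degludec the comparison for safety measures unless something else is specified. In Section 5.10.3.2, the footnote to Table BDCP.1 places the post-treatment analyses on the Safety Population, and for the rest: "analyses for endpoints during other time points will include all data before study drug discontinuation on Safety population". Severe hypoglycemia is to be listed and compared by Fisher's exact test, with no population named.

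The SAP Revision History describes the removal of Algorithm 2 as an alignment with protocol amendment (d). It mentions the pooled comparison only as an added sensitivity analysis.

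**The concern.** The two documents name different populations for the same analyses, and the difference decides who counts as LY3209590. The protocol compares participants randomized to Algorithm 1, the dosing regimen that continues, with insulin degludec. The SAP compares a mixture of Algorithm 1 and Algorithm 2 with insulin degludec.

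Incidence and rate of hypoglycemia during treatment is a secondary safety endpoint in both documents. Hypoglycemia depends directly on dosing, and the protocol's amendment rationale says Algorithm 2 was stopped because of problems with its dosing recommendations and frequent investigator overrides. That is a reason to report the continuing regimen separately. It does not show which way pooling would move the result.

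At stake is whether the protocol-specified comparison is produced at all, and whether a change of population in an open-label trial with an unblinded study team is declared. Pooling for adverse events, laboratory measures and the other safety tables follows the protocol and is not questioned.

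**Working it through.** The plan gives no figure for this point, so the check is mainly a comparison of texts.

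**1. Population by analysis**

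| Diary hypoglycemia analysis | Protocol 9.4.6.3 | SAP 5.10.3.2 |
|---|---|---|
| Level 1, Level 2/3 during treatment (0-12, 12-26, 0-26 weeks) | Efficacy | Safety (footnote) |
| Level 1, Level 2/3 after treatment | Efficacy | Safety (footnote) |
| Severe (level 3) | Efficacy and Safety | None named; the Safety default in 5.10 applies |
| HbA1c target without nocturnal hypoglycemia, 0-26 weeks | Not listed by name | Safety (footnote, or the 5.10 default) |

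For Level 1 and the Level 2/3 composite the conflict is complete. For level 3 alone the protocol foresees the Safety Population analysis, and only the Efficacy Population version is missing.

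**2. Does the choice of population change the comparison?** Yes. The SAP's own Efficacy Population is "All participants randomized to either LY3209590 Algorithm 1 or insulin degludec and took at least 1 dose of study treatment", so it has no Algorithm 2 participants. The Safety Population includes them as LY3209590.

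**3. Does another part of the SAP supply the missing result?** Not clearly.
- CGM-derived hypoglycemia (SAP 5.1 and 5.11) is restricted to Algorithm 1 versus insulin degludec, but it is a different endpoint. CGM episodes need at least 15 minutes below threshold and define night as midnight to 0600. Diary events are glucose readings, with nocturnal meaning between bedtime and waking.
- The subgroup analysis of hypoglycemia rates (SAP 5.12) names no population.

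**4. Is the change declared?** No. The Revision History lists analysis population only generically, as an example of added detail. No text says that the hypoglycemia population differs from Protocol 9.4.6.3 or gives a reason.

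**5. Possible size, on assumptions only.** The documents give about 119 participants planned for Algorithm 1 (Protocol 9.2). They give no Algorithm 2 count and no event rates. Let n2 be the number of Algorithm 2 participants, k their event rate relative to Algorithm 1, and f the share of their exposure that carries that rate, with equal exposure per participant. In crude rates:

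multiplier = pooled LY3209590 rate / Algorithm 1 rate = 1 + w × f × (k − 1), with w = n2 / (119 + n2).

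The insulin degludec rate does not change, so the LY3209590/degludec rate ratio is multiplied by the same factor. For example, with n2 = 40, k = 3 and f = 1: w = 40/159 = 0.252, and 1 + 0.252 × 2 = 1.503 (unrounded w).

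| n2 | w | f = 1: k = 0.5 to k = 3 | f = 0.25: k = 0.5 to k = 3 |
|---|---|---|---|
| 5 | 0.040 | 0.980 to 1.081 | 0.995 to 1.020 |
| 15 | 0.112 | 0.944 to 1.224 | 0.986 to 1.056 |
| 40 | 0.252 | 0.874 to 1.503 | 0.969 to 1.126 |

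With k = 1 the multiplier is 1.000 for any n2 and f. A value of f below 1 is allowed because the protocol's summary of changes says that Algorithm 2 participants proceed with the procedures for those treated with LY3209590, so only part of their exposure may reflect Algorithm 2 dosing.

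**The case against.** - **Delegation to the SAP.** Protocol 9.4.1 leaves the details of the hypoglycemia analyses to the SAP, so the sponsor could say that the population is one of them. This does not cover the switch, because Protocol 9.4.6.3 itself names the population.
- **Deliberate and consistent pooling.** The SAP post-dates amendment (d). It states the pooled rule in 5.1, 5.10 and the footnote, and separates only the CGM measures. This suggests that pooling may have been considered. It may equally be carried-over wording, and the documents do not settle which. Either way a justification is missing. SAP 5.1 would allow it to appear in the clinical study report alone, but the protocol asks for it in both documents.
- **The HbA1c composite rows.** The rate and incidence cells carry their own asterisk and the composite cell does not, so the footnote might not reach those rows. But the asterisk also stands on the time-point column header, 0-26 weeks is one of the other time points, and without the footnote the pooled default in 5.10 would still apply. The protocol does not list this composite among its endpoints, so applying 9.4.6.3 to it is an inference.
- **Weight.** Including every dosed participant in a safety comparison is defensible, Algorithm 1-only CGM results will exist, and the protocol describes a limited number of Algorithm 2 participants. These points limit the practical effect but do not remove the contradiction.

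**Conclusion.** The concern holds and should be fixed. As written, the SAP would not produce the protocol-specified Algorithm 1 versus insulin degludec analysis of diary hypoglycemia, and it does not identify the change as a departure. This rests on the text of the two documents and needs no numerical assumption.

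The effect on the estimate is unknown in size and direction. The multiplier of 0.87 to 1.50 depends entirely on assumed values for n2, k and f. With few Algorithm 2 participants it lies close to 1, so the effect may be small.

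**What to change.** Revise the Table BDCP.1 footnote as follows:

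- Put the Level 1 and Level 2/3 rate and incidence analyses, for all three treatment intervals and the post-treatment period, on the Efficacy Population (Algorithm 1 versus insulin degludec). Do the same for the two HbA1c-without-nocturnal-hypoglycemia rows.
- Analyse severe (level 3) hypoglycemia on both the Efficacy and the Safety Population, as Protocol 9.4.6.3 states.
- Use one definition of the Efficacy Population. Protocol 9.3 has no dosing requirement, whereas SAP 5.1 requires at least one dose.
- Keep the pooled Safety Population versions of the diary tables as supplementary output, and leave the other pooled safety tables unchanged.

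If pooling was intended, say so and justify it in the SAP and the clinical study report, and still provide the Algorithm 1 analysis.

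The cost is a revision of the SAP text, a population flag for the diary hypoglycemia tables and a second set of those tables. No new data are needed.

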5.10.3.3. Hepatobiliary Events

The percentages of patients with treatment-emergent hepatic AEs will be summarized by treatment group using MedDRA PT nested within each SMQ ordered by decreasing frequency. The following SMQs based on MedDRA will be used to identify hepatic events:

- Broad and narrow terms in the Liver related investigations, signs and symptoms SMQ (20000008)
- Broad and narrow terms in the Cholestasis and jaundice of hepatic origin SMQ (20000009)
- Broad and narrow terms in the Hepatitis non-infections SMQ (20000010)
- Broad and narrow terms in the Hepatic failure, fibrosis and cirrhosis and other liver damage SMQ (20000013)
- Narrow terms in the Liver-related coagulation and bleeding disturbances SMQ (20000015)

5.10.3.4. Injection Site Reactions

Injection site reactions will be evaluated using the spontaneous AE reporting of injection site reactions by the selected MedDRA PTs for the LY3209590 study program.

[Table BDCP.2](#) contains a list of MedDRA PTs based on MedDRA (both narrow and broad scope) that will be used to identify potential injection site reaction from the spontaneous reported AEs.

The number and percentage of patients experiencing treatment-emergent potential injection site reaction identified using MedDRA PT search strategy will be summarized and compared by treatment group using Fisher's exact test. The number and percentage of patients experiencing treatment-emergent potential injection site reactions that is judged to be related to study drug by the investigator will also be summarized and compared.

Table BDCP.2. List of MedDRA Preferred Terms (PTs) to Search for Injection Site Reaction Adverse Events (AEs)

Preferred Term	Preferred Term Code	Scope
Injection site abscess	10022044	Narrow
Injection site abscess sterile	10022045	Narrow
Injection site atrophy	10022048	Narrow
Injection site erythema	10022061	Narrow
Injection site hypertrophy	10022072	Narrow
Injection site induration	10022075	Narrow
Injection site infection	10022076	Narrow
Injection site inflammation	10022078	Narrow
Injection site irritation	10022079	Narrow
Injection site mass	10022081	Narrow
Injection site edema	10022085	Narrow
Injection site pruritus	10022093	Narrow
Injection site rash	10022094	Narrow
Injection site reaction	10022095	Narrow
Injection site warmth	10022112	Narrow

Preferred Term	Preferred Term Code	Scope
Injection site cellulitis	10050057	Narrow
Injection site swelling	10053425	Narrow
Injection site discomfort	10054266	Narrow
Injection site nodule	10057880	Narrow
Lipoatrophy	10024604	Narrow
Lipodystrophy acquired	10049287	Narrow
Partial lipodystrophy	10053857	Narrow
Lipohypertrophy	10062315	Narrow
Injection site bruising	10022052	Broad
Injection site haematoma	10022066	Broad
Injection site haemorrhage	10022067	Broad
Injection site pain	10022086	Broad

5.10.3.5. Systemic Hypersensitivity Reaction

The number and proportion of patients experiencing potential treatment-emergent systemic hypersensitivity reactions will be summarized and compared by treatment group using Fisher's exact test. The following MedDRA Standardized MedDRA Query (SMQ) will be used to identify potential systemic hypersensitivity reactions from all TEAEs:

- Anaphylactic reaction (SMQ). Besides using the narrow and broad terms designated within the SMQ, the following search algorithm will also be implemented as another approach to determine if a patient had an anaphylactic reaction: if a patient (had at least 1 event in Category A) or (had at least 1 event that is in Category B and also had at least 1 event that is in Category C) or (had at least 1 event that is in Category D and [also had at least 1 event in Category B or at least 1 event in Category C])
- Angioedema (SMQ)
- Hypersensitivity (SMQ)

Specifically, need to perform the following: (1) any narrow or algorithmic term from any 1 of the 3 SMQs indicated above (i.e., combined search across narrow and algorithmic portions of all 3 SMQs); (2) any narrow scope term within each SMQ, separately (i.e., narrow SMQ search); (3) any term within each SMQ, separately (i.e., broad SMQ search); (4) narrow scope term search within each SMQ, report the PT nested within each SMQ.

Note that an individual patient may contribute multiple events. Also, a single event may satisfy multiple SMQs, in which case the event contributes to every applicable SMQ.

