10.9. Appendix 9: Recommended Laboratory Testing for Hypersensitivity Events

Guidance for laboratory assessments for hypersensitivity events:

Laboratory assessments should be performed if the participant experiences generalized urticaria or if anaphylaxis is suspected.

- Collect sample after the participant has been stabilized, and within 1 to 2 hours of the event; however, samples may be obtained as late as 12 hours after the event as analytes can remain altered for an extended period of time. Record the time at which the sample was collected.
- Obtain a follow-up sample at the next regularly scheduled visit or after 4 weeks, whichever is later.

Table 3.

Clinical Lab Tests for Hypersensitivity Events

CCI

10.10. Appendix 10: Changes to Study Procedures due to the COVID-19 Pandemic or Natural Disasters

Remote Visits during the Study

If COVID19- or natural disaster-related travel or shelter-in place restrictions are requested by local/regional authorities or for other reasons related to the pandemic or natural disasters which make it impossible for the participant to travel to the study site for the mandatory titration visits, mitigations are required to ensure safe and timely dosing of study participants.

The study site must receive prior approval by Lilly for either site mobile visits performed by trained site personnel or visits performed by a qualified home nursing service provider organized by the sponsor, with video-conferencing ability, to replace the on-site visits.

Protocol procedures, including blood draws, data-downloads, participant (re-) education, study drug dose selection and study drug dosing may be performed at the participants' home by qualified personnel until travel or other restrictions are lifted.

The allowed visit windows can be extended based on advice from Lilly Medical in this exceptional case to allow more flexibility in performing the home visits.

Early Discontinuation Procedures:

If a participant is quarantined or contracts COVID-19 or is unable to attend the visit for other reasons during the course of the study and therefore mobile visits cannot be organized, study treatment must be discontinued early and dosing decisions for the alternative treatment are allowed to be performed by telephone.

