5.10.2. Adverse Events

Adverse events will be summarized as TEAEs (defined as events that are newly reported after the first dose of study basal insulin or reported to worsen in severity from baseline) and compared between treatments unless otherwise specified. The Medical Dictionary for Regulatory Activities (MedDRA) Lowest Level Term (LLT) will be used in determining the treatment-emergent status. The maximum severity for each LLT during the baseline period will be used as baseline severity. All analysis will be performed on the data collected from the date of first dose of study drug (or the randomization visit date if date of first dose is not available) to the end of the study (up to Visit 801).

The incidence of patients with at least 1 TEAE and the incidence of TEAEs by PT and system organ class (SOC) will be presented by treatment group. The number and percentage of patients

with TEAEs will be summarized by treatment using MedDRA PTs nested within SOC. Events will be ordered by decreasing frequency within SOC.

The number and percentages of patients with TEAEs ($\geq 2\%$ before rounding) will be summarized by treatment using MedDRA PT (without regard to SOC). Events will be ordered by decreasing frequency.

The incidence of participants with at least 1 TEAE assessed as possibly related to the IP will be summarized by treatment group using MedDRA PT nested within SOC. Events will be ordered by decreasing frequency within SOC. In addition, a summary of TEAEs by maximum severity will be presented descriptively by treatment group.

Discontinuations due to AEs will be summarized by PT and compared between treatment groups using Fisher's exact test for the Safety Population.

All SAEs (including death) will be listed by patient for the Safety Population.

Summary of TE-SAEs similar to summaries for the proportion of patients experiencing each reported TEAE by SOC will be included for the Safety Population.

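### SAP 5.10.3.5 pairs Category B, C and D events per patient with no time condition, so unrelated events months apart can count as a potential anaphylactic reaction in the combined hypersensitivity search

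*SAP*

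**What the plan says.** SAP 5.10.3.5 searches all treatment-emergent adverse events with three standardized queries: Anaphylactic reaction, Angioedema and Hypersensitivity. For the first it adds an algorithm, described as "another approach to determine if a patient had an anaphylactic reaction". A patient meets it in any of three ways:

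- at least one Category A event;
- Category B with Category C: the patient "had at least 1 event that is in Category B and also had at least 1 event that is in Category C";
- at least one Category D event together with at least one from B or C.

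The conditions are set at patient level. None refers to onset date, episode or interval.

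The section lists four outputs. Search (1) is "any narrow or algorithmic term from any 1 of the 3 SMQs indicated above". Searches (2) to (4) are the narrow search per query, the broad search per query, and narrow preferred terms nested within query. Patient counts are compared between arms by Fisher's exact test. The section's stated purpose is modest: the queries "will be used to identify potential systemic hypersensitivity reactions from all TEAEs".

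The period searched comes from SAP 5.10.2: "All analysis will be performed on the data collected from the date of first dose of study drug", ending at Visit 801.

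**The concern.** An algorithm that combines symptoms from different categories is meant to catch one reaction recorded as several adverse events. That only works if the events belong together. As written, a Category B event in Week 2 and an unrelated Category C event in Week 25, 23 weeks or 161 days apart, make the patient a match. A programmer following the text would apply no window. Elsewhere the SAP does state such conditions: a CGM hypoglycemic episode needs a minimum duration (5.11.3.2), and parts of the liver listing need consecutive abnormal tests (5.10.5.2).

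Allergic and hypersensitivity reactions are adverse events of special interest in Protocol 8.3.7. Chance matches would inflate the combined count. They also depend on products of incidences, so they grow faster than ordinary event reporting. If one arm of this open-label trial reported more ordinary events, the rule would exaggerate that difference.

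**Working it through.** **Is there a time condition anywhere?** SAP 5.10.3.5 has none. SAP 5.10.2 sets only the overall period. Protocol 8.3.7.2 and 8.3.7.3 govern reporting and extra data collection, and Protocol 9.4.6.6 asks for descriptive statistics. Appendix 9 governs laboratory sampling. No section limits the pairing, and none requires matches to be reviewed or adjudicated. The plan states no figure on this point, so there is none to reproduce.

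**Length of the period.** Protocol 4.1 gives 26 weeks of treatment and 5 weeks of follow-up: 26 + 5 = 31 weeks, or 31 × 7 = 217 days.

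**How far apart are chance pairs?** Assume two unrelated onsets, independent and uniform over 217 days.

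- Within ±1 day: (217 + 2 × 216) / 217² = 649 / 47,089 = 1.4%.
- More than 28 days apart: (1 − 28/217)² = 76%.
- More than 60 days apart: (1 − 60/217)² = 52%.

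This result does not depend on the incidences: almost all chance pairs are far apart.

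**How many chance matches?** The documents give neither the contents nor the incidence of Categories B, C and D. Let pB, pC and pD be assumed, independent probabilities of at least one event per patient over the period. The chance of a B+C or D+(B or C) match is

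P = pB·pC + pD·[pB(1 − pC) + pC(1 − pB)].

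For 5/5/2%: 0.0025 + 0.02 × 0.095 = 0.0044. Expected matches are 238 × P, and the chance of at least one is 1 − (1 − P)^238. Here 238 is the planned number for the two remaining arms (Protocol 9.2), used for illustration; the Safety Population also includes dosed participants from the closed Algorithm 2 arm.

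With a ±1 day window and one event per category, expected matches are at most 238 × (649/47,089) × (pB·pC + pB·pD + pC·pD).

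| Assumed B/C/D | P, no window | Expected in 238 | Chance of any | Expected, ±1 day |
|---|---|---|---|---|
| 1/1/0.5% | 0.020% | 0.05 | 5% | 0.0007 |
| 2/2/1% | 0.079% | 0.19 | 17% | 0.003 |
| 5/5/2% | 0.44% | 1.05 | 65% | 0.015 |
| 15/10/5% | 2.60% | 6.19 | 99.8% | 0.090 |

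The window cuts chance matches about 70-fold (for example 6.19 / 0.090 = 69).

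**Effect of unequal reporting.** Doubling 5/5/2% to 10/10/4% gives P = 0.01 + 0.04 × 0.18 = 0.0172, against 0.0044. That is about 3.9 times as many chance matches for twice the incidence.

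**The case against.** The strongest reply is that this is a screen, and only part of one. The section calls its hits potential reactions, and the algorithm supplements the narrow and broad searches. It enters only search (1), where it is joined with all narrow terms from three queries. The SAP lists no stand-alone count of algorithmic anaphylaxis. That stands, and it limits the consequence.

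A reader might go further and infer that chance pairs would form most or all of the algorithmic cases, that the arm comparison would be noise, or that at least one false case is likely. The documents do not support this. The share of search (1) made up of chance matches cannot be estimated from them, and at 2/2/1% or below a chance match is unlikely. Protocol 10.3.3 also prefers a diagnosis over separate signs and symptoms, which may leave fewer entries to pair.

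A reader might also take Appendix 9 as defining the interval, since it says "Collect sample after the participant has been stabilized, and within 1 to 2 hours of the event". That sentence governs laboratory sampling, not the pairing of adverse event records.

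Investigators must report hypersensitivity reactions and give symptom-level data for systemic ones (Protocol 8.3.7.2 and 8.3.7.3), so the safety assessment does not rest on this algorithm. However, the SAP does not require matches to be checked against those data.

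Finally, a hard window could lose a true case with a misrecorded onset date. This is a fair objection to a bare window, and the listing proposed below answers it.

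None of these replies supplies the missing condition. Calling a hit potential does not make two events months apart one reaction.

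**Conclusion.** The point holds as a minor defect that is cheap to repair. Applied as written, the rule counts unrelated events up to about 31 weeks apart as a potential anaphylactic reaction and carries them into search (1). Searches (2) to (4) and the primary HbA1c analysis are untouched, and SAP 5.10.3.5 attaches no decision rule to the result.

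The gap in the text is certain; its numerical effect is not. The range of about 0.05 to 6.2 expected chance matches in 238 rests on assumed incidences and on independence between categories. The finding that only about 1.4% of chance pairs fall within ±1 day needs no incidence, but it does assume independent onsets spread evenly over 217 days.

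**What to change.** In SAP 5.10.3.5, add that Category B, C and D events combined by the algorithm must have onset within a short prespecified window, for example the same or next calendar day. The documents do not fix a window, so the sponsor should choose and justify it. Treat partial onset dates as matching unless the window can be excluded. List patients who meet the pairing rule only outside the window for medical review, so that a misdated true case is not lost. Leave the Category A criterion and the narrow and broad searches unchanged.

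The cost is a sentence or two in the SAP, a date condition in the program, a partial-date rule and one short listing. The remaining downside is a small possible loss of sensitivity in the count, which the listing offsets.
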